The first 20-30 minutes of the initial laboratory visit is devoted to walking the participant through the procedures and risks of the study, as well as answering any questions they might have prior to signing the informed consent document. Participants will then be asked to complete a series of questionnaires including: a 1-page health screening (AHA/ACSM Health/Fitness Facility Preparticipation Screening Questionnaire), 1-page Physical Activity Questionnaire, and a 1-page Demographic Questionnaire (Race and Ethnicity Questionnaire). The participant will also complete a body composition analysis as described below.

Measurement of muscle and fat tissue using bioelectrical impedance analysis: This test simply involves standing on a scale with your feet and hands on sensors for a few seconds. A very low electrical current that you cannot feel and that is not dangerous is transmitted and received across the sensors. The technology is commonly used in a variety of settings such as gyms and health screenings, but the instrument that we will use is more sophisticated in being able to estimate muscle and fat tissue in different regions of your body, including the abdominal cavity that is particularly important for predicting risk of diabetes.

Visit 2:

During Visit 1, our team will work with participants to determine an appropriate meal (breakfast or lunch) to eat that contains approximately 50 g of fat and to schedule a visit (Visit 2) approximately 3-4 hours after consuming this meal. Participants will come to the lab and have blood drawn according to standard procedures, where briefly blood is collected via venous puncture from a forearm vein.

Random Assignment: Participants will be randomized into Pulse or Control groups after Visit 2 if their non-fasting serum TG concentration 3-4 hours after a meal of the participant's choosing is greater than 175 mg/dl. Individuals with non-fasting TG levels less than 175 mg/dl will not complete the 12 week dietary intervention and will receive the benefits that were a part of their conducted visits in addition to monetary payments, prorated to the their total time spent in the study.

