Self-Collected Stool Sample: A stool sample will be used to analyze the types of microbes present in the gut. The analysis involves measurement of the genetic material of the bacteria. This does not give us any information about the individual's genetic material, only that of the bacteria in their gut. They will be given three self-collection kits that each come with printed step-by-step instructions to collect their stool sample. Two kits will be given at visit 2 for stool sample delivery at Visit 3. An additional kit will be given towards the end of the study in coordination with a meal pick-up for stool sample delivery at Visit 4.

Biospecimen Analysis

All blood and fecal specimens collected during Visits 3 and 4 are de-identified at the point of collection and remain de-identified for the duration of testing and analysis.

Stool samples are sent to the University of Michigan through [name] lab for 16S analysis. De-identified, un-processed, microbial DNA results are electronically sent back to MSU Nutrition Lab for data processing and analysis. Serum samples for metabolomic analysis are sent to [name] lab where de-identified results are processed and analyzed. Results are electronically sent back to MSU Nutrition Lab for additional analysis. Remaining biomarker analyses including inflammation, lipid, and blood glucose levels are processed and analyzed in the MSU Nutrition Research Lab as de-identified specimens.

All biospecimen results remain de-identified through study publication.

Statistical Plan

Habitual dietary patterns, represented by DHQ-III HEI scores, were analyzed at base-line through general linear models to detect existing dietary differences between meal groups. Diet components expected to change with a lentil-based intervention including total fiber g, insoluble fiber g, and legumes (cups) as well as total energy intake (kcals) were also assessed for baseline differences. To determine if intervention meal consumption changed participant dietary intake, linear mixed effects models were used to assess dietary components and HEI scores with an interaction predictor between meal and time (pre- or post- intervention) and a random effect for subject. Post-hoc multiple pairwise comparisons were performed to detect significant differences by group using Tukey's HSD.

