Linear mixed effects models were used to assess the impact of a week and meal interaction on satiety measures. GI symptom severity was analyzed through a linear mixed effects model with symptom type and a week and meal interaction as predictors. Subject was the random effect for models assessing satiety and GI symptom severity.

Descriptive summary statistics were performed for participant physical and biological characteristics with general linear models used to determine if participants on average differed between meal groups before the intervention began. General linear models were used to assess

the impact of the dietary intervention on the following categories of variables: anthropometric measures (weight, fat mass percent, visceral adipose, and waist circumference); fasting blood lipid measures (CHOL, HDL, LDL, TG); fasting glycemic measures (GLU, INS, HOMA-IR); and fasting inflammation markers (GM-CSF, IFN- γ , TNF- α , IL-1 β , IL-6, IL-10, IL-17, IL-23). Fasting inflammation markers were normalized using r package bestNormalize [38] prior to statistical analysis. Dependent variables were calculated as the change in values from baseline (post-intervention – pre-intervention). Predictor variables were shared within each category of variables and are as follows: anthropometric measures –meal group; blood lipid measures –meal group, visceral adipose tissue; glycemic measures –meal group, visceral adipose tissue, change in BMI, HbA1c; inflammation measures –meal group, visceral adipose tissue. Predictor variables for glycemic measures were chosen based on previous findings by Zeevi and colleagues [39].

Analysis of postprandial metabolic (TG, GLU, INS) and inflammatory (GM-CSF, IFN- γ , TNF- α , IL-1 β , IL-6, IL-10, IL-17, and IL-23) measures were conducted by summarizing each makers measurements at timepoints 0 (fasting) and 1, 2, 3, 4, and 5 hours postprandially as net area under the curve (AUC) using the auctime [40] R package. Each dependent variable was then summarized as the change in AUC (post-intervention – pre-intervention). AUC values for inflammation markers were normalized using r package bestNormalize [38] prior to statistical analysis. General linear models were used to assess the impact of intervention meal group on each dependent variable. Predictor variables were identical to variables utilized in corresponding fasting models.

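### For dietary intake and HEI scores, the only step named for detecting differences is Tukey pairwise comparison, and no such pair is the between-arm difference in change

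*Combined protocol and SAP*

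**What the plan says.** The first paragraph of the Statistical Plan sets the question and the model: "To determine if intervention meal consumption changed participant dietary intake, linear mixed effects models were used to assess dietary components and HEI scores", fitted "with an interaction predictor between meal and time (pre- or post- intervention) and a random effect for subject". The next sentence is the only one that describes detecting anything: "Post-hoc multiple pairwise comparisons were performed to detect significant differences by group using Tukey's HSD".

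The components of interest appear earlier in that paragraph, for the baseline check: "total fiber g, insoluble fiber g, and legumes (cups) as well as total energy intake (kcals) were also assessed for baseline differences". There are two arms (Visit 2, Random Assignment): "Participants will be randomized into Pulse or Control groups after Visit 2".

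The plan does not say that the interaction coefficient is tested, reported with an interval or used as the criterion. It does not say which means enter the Tukey family, and it gives no significance level. Nor does it say that the Tukey step replaces a test of the interaction.

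The third paragraph takes another route for anthropometric and fasting blood measures: "Dependent variables were calculated as the change in values from baseline (post-intervention – pre-intervention", regressed on meal group. Postprandial measures are handled in the same way, as change in AUC.

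**The concern.** In a two-arm randomised trial measured before and after, the question whether the meals changed intake is answered by one contrast: change in the Pulse arm minus change in the Control arm. The fitted model contains it, but the step named for finding differences does not test it. Pairwise comparisons give within-arm changes, single-time arm differences and, if all four cells are compared, two cross-pairs that answer no question.

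At stake is the evidence that the arms separated on fibre and legumes, and whether energy intake or overall diet quality also moved differently. A finding that intake changed in the Pulse arm but not in Control is not a test that the changes differ. A common shift is plausible: under Dietary intervention, both arms receive provided midday meals, and participants, with no restriction by arm, are told to cut evening portions.

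**Working it through.** **Inputs.** From the documents: 2 arms, 2 times, a random subject effect. Not in the documents, so assumed: two-sided 0.05, equal arms, n = 15, 20 or 40 per arm, SD = 1, pre-post correlation ρ = 0.3, 0.5 or 0.7, a true difference in change of 0.8 SD where power is computed, and no dropout. The plan has no power figure to reproduce.

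**1. Contrasts.** Two arms by two times give 4 cells and 4 × 3 / 2 = 6 pairs. Each pair involves two cells. The difference in change has weights (+1, −1, −1, +1) on all four. So no pair equals it, whatever the assumptions. If the family is instead the arms within each time, there is one comparison per time and no Tukey penalty, but a single-time difference is still not the difference in change.

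**2. Power.** Standard errors:
- interaction: √(2(1−ρ)) × √(2/n)
- post-intervention arm difference: √(2/n)
- within-Pulse change: √(2(1−ρ)) × √(1/n)

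At n = 20 the critical values are 2.024 for the single contrast and 2.686 for Tukey over four means. With the Control arm unchanged, the noncentrality of the post-intervention difference is 0.8/√(2/20) = 2.53. The other two depend on ρ. Powers are from 20,000 simulated trials per setting.

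| ρ | Interaction: noncentrality | Interaction: power | Post-intervention difference, Tukey: power | Within-Pulse: noncentrality | Within-Pulse, Tukey: power |
|---|---|---|---|---|---|
| 0.3 | 2.14 | 0.55 | 0.46 | 3.02 | 0.63 |
| 0.5 | 2.53 | 0.70 | 0.47 | 3.58 | 0.81 |
| 0.7 | 3.27 | 0.89 | 0.46 | 4.62 | 0.97 |

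For the post-intervention difference under Tukey, the loss against the interaction test runs from about 1 point (n = 40, ρ = 0.3: 0.84 against 0.85) to 46 points (n = 15, ρ = 0.7: 0.32 against 0.78). Without the Tukey penalty it has the same noncentrality as the interaction at ρ = 0.5, a larger one below that and a smaller one above. The within-Pulse comparison beats the interaction test in every setting, because its standard error is smaller by a factor of √2.

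**3. Significance in one arm only, with no true difference in change.** If each within-arm test is significant with probability p, the chance that exactly one is significant is about 2p(1−p). At n = 20 and ρ = 0.5:

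| Common change in both arms (SD) | p | 2p(1−p) | Simulated |
|---|---|---|---|
| 0 | 0.011 | 0.02 | 0.02 |
| 0.3 | 0.103 | 0.18 | 0.18 |
| 0.5 | 0.340 | 0.45 | 0.42 |
| 0.8 | 0.804 | 0.32 | 0.30 |

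The simulated values fall slightly below the formula because both tests share one error estimate. About half of these cases are Pulse-only (0.21 of the 0.42). The interaction test rejects in about 5% at every common change.

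**4. Post-intervention arm difference under the same null.** Under Tukey it is significant in about 1% of trials, so randomisation keeps its error rate low. It takes no account of a chance imbalance at baseline, however, and pairing significance after the intervention with non-significance before it is again not a test of the difference in change.

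**The case against.** The strongest reply is that the right quantity is already in the plan. The stated purpose is attached to the interaction model, the interaction coefficient in a 2 × 2 layout is the difference in change, and calling the Tukey step post hoc suggests that it follows a test of that coefficient. This stands in part. A reader might infer that Tukey replaces the interaction test, but the text does not say so. Equally, it never says that the interaction is tested or decides anything.

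The four-cell family is also an inference. It is the natural one, because Tukey's method has no work to do with two means, but the wording could mean arms within each time. The contrast argument holds under either reading.

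A reader might further infer that the plan loses power across the board. The working shows otherwise: the loss applies to the post-intervention arm difference, while the within-Pulse comparison gains power and fails on validity.

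The one-arm-only rates also need care. 2p(1−p) cannot exceed 50% for any pair of independent tests, the rate is about 2% when neither arm changes, and it falls towards zero when both arms change so much that both tests are significant. They show what a particular inference would cost, and the plan does not say that it will draw that inference.

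**Conclusion.** The point holds as one of validity and specification. The plan names pairwise comparisons as the way to detect differences, none of them is the difference in change, and the family is undefined. The algebra needs no assumption. The sizes depend on assumed n, significance level, SD, correlation and effect, none of which the documents give, so they are illustrations only.

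The scope is the dietary-component and HEI analyses, which are supportive. A reader might infer that the triglyceride and inflammation conclusions are affected. They are not: those analyses, like the glycemic and anthropometric ones, regress change on meal group, and no intake variable is among their predictors. Nor do the documents support the inference that energy intake must stay unchanged for the trial to be interpretable, since Dietary intervention tells participants to eat smaller evening meals. Clarifying the rule is worthwhile because it costs little and brings the diet analyses into line with the rest of the plan.

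**What to change.** Replace the Tukey sentence with wording such as:

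> For each dietary component and HEI score, the test of intervention effect is the single meal × time interaction contrast (change in the Pulse group minus change in the Control group), reported with its estimate, 95% confidence interval and p-value. Pairwise and within-group comparisons are descriptive follow-up; the set of comparisons covered by any Tukey adjustment is stated.

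The contrast is already a coefficient of the planned model, so no new data or model is needed. Because the plan is written in the past tense, any results already produced can be re-reported from the same fits. The only loss is the pairwise significance labels in the diet tables.

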Dietary intervention: Using methods we have established for an ongoing randomized clinical trial with 8 weeks of lentil supplementation, we will prepare 7 mid-day meals per participant per week to deliver a dose of 0 or 3 cups of lentils per week for the experimental and control groups. Meals are matched for macronutrient content (except for fiber), and ground turkey replaces lentils in the control meals. Participants will be instructed to consume food provided for their midday meal, and then to proactively reduce portion sizes and to not eat beyond fullness at the evening meal. This strategy exploits the satiety effect of pulses at the midday meal and the 'second meal effect' in which volitional consumption is reduced at the next meal, the evening meal.

A brief 4 pm online survey addressing satiety and a brief 8 PM online survey addressing gastrointestinal issues will be delivered once a week during the 12-week intervention to participants through personalized e-mails or texts. Each participant will be surveyed once weekly to determine whether they consumed the experimental meal that day, their perceptions of hunger, fullness, satiety, and satisfaction with that day's meal (at 4:00 pm), and their gastrointestinal comfort (level of bloating, flatulence, cramping, and comfort) throughout the day (at 8:00 pm). This methodology has been successfully implemented in our ongoing study to demonstrate that lentil meals are equally pleasing, produce greater satiety, and are well-tolerated.

Vist 3 and 4:

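### The satiety and GI models name only a week-by-meal interaction, to which a constant lentil-control difference adds nothing once main effects are fitted, and no averaged contrast is named

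*Combined protocol and SAP*

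**What the plan says.** The Statistical Plan describes the satiety analysis in one sentence: "Linear mixed effects models were used to assess the impact of a week and meal interaction on satiety measures". For gastrointestinal symptoms it says: "GI symptom severity was analyzed through a linear mixed effects model with symptom type and a week and meal interaction as predictors". Subject is the random effect in both. For these outcomes the plan names no meal main effect, no lentil-minus-control contrast and no coding of week.

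The surveys are set out under Dietary intervention in the Study Protocol: they "will be delivered once a week during the 12-week intervention". No survey before the first study meal is described.

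Two nearby parts of the Statistical Plan are useful for comparison. The diet-intake models are specified "with an interaction predictor between meal and time (pre- or post- intervention) and a random effect for subject", and that text closes with "Post-hoc multiple pairwise comparisons were performed to detect significant differences by group" by Tukey's method. The change-score models for anthropometric, lipid, glycemic and inflammation outcomes each list meal group itself as a predictor.

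**The concern.** A group-by-time interaction equals the treatment effect when one of the times is before treatment. That holds for the diet-intake models, where time is pre or post. It does not hold for the surveys as described, because every survey week falls within the intervention. There, the interaction asks only whether the gap between groups changes from week to week after the meals have begun.

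A satiety or GI effect that starts with the first meals and persists is a difference in level. The feeding rationale points that way: "This strategy exploits the satiety effect of pulses at the midday meal". That places the effect at the meal itself, with no mention of a build-up over weeks. The one named test would not see such an effect, and its non-significance could be misread as evidence that the meals are equally satiating or equally well tolerated.

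**Working it through.** The plan states no figure on this point, so there is none to reproduce. The core is algebra. The power figures only illustrate it.

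**Inputs.** From the documents: two groups, 12 weekly surveys, a random effect for subject. Assumed, because the documents do not give them: 20 or 30 per arm, total variance 1, ICC 0.5 (range 0.3 to 0.7), two-sided alpha 0.05, complete surveys, constant difference d = 0.5 SD unless stated.

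**1. What the interaction tests.** Let D(w) be the expected lentil-minus-control difference in week w, for w = 1 to 12, with both main effects fitted.
- Week as a factor: the test is whether D(w) minus its 12-week mean is zero in every week. If D(w) = d throughout, each term is d − d = 0.
- Week as a number: the coefficient is Σ(w − 6.5)D(w)/143, where 143 = Σ(w − 6.5)². If D(w) = d, this is d × 0/143 = 0.
- The average contrast is ΣD(w)/12 = 12d/12 = d.

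**2. Comparison with the diet-intake models.** With a pre value at which the groups are expected to be equal and a post difference of d, meal-by-time is d − 0 = d. The same kind of term carries the whole effect there and none of a constant effect here.

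**3. Rejection rates for the interaction.** Simulation, 8,000 runs, ICC 0.5:

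| Constant difference | Week coding | n = 20 | n = 30 |
|---|---|---|---|
| 0.5 SD | numeric | 0.055 | 0.047 |
| 0.5 SD | factor | 0.053 | 0.052 |
| 1.0 SD | numeric | 0.050 | 0.050 |
| 1.0 SD | factor | 0.045 | 0.053 |

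A separate run of 4,000 at 2 SD and 30 per arm gave 5.1% under both codings.

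**4. The average contrast.** The variance of a subject's 12-week mean is ICC + (1 − ICC)/12 = 0.5 + 0.5/12 = 0.542. The standard error of the group difference is √(2 × 0.542/n), which is 0.233 at n = 20 and 0.190 at n = 30. Noncentral-t power at 0.5 SD is 0.553 and 0.735, and the 95% CI half-width is 0.471 and 0.380 SD. Over the ICC range and both sample sizes, power runs from 0.440 to 0.889 and half-width from 0.309 to 0.545 SD.

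**5. If main effects were omitted.** With numeric week and a common intercept, a constant d is forced into a difference in slopes. Under the random-intercept model at ICC 0.5, Σw = 78. The fitted slope difference is d × [78/(0.5 + 12 × 0.5)] / [143/0.5 + 12 × 6.5²/6.5] = 0.5 × 12/364 = 0.0165 per week. The fitted gap is then 0.0165 SD at week 1 and 0.198 SD at week 12, with mean 6.5 × 0.0165 = 0.107 against a true 0.5. Power is 0.169 at n = 20 and 0.230 at n = 30. With week as a factor, the model is a set of cell means that contains the difference, but a contrast still has to be named to extract it.

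**The case against.** The wording is probably shorthand for a full week-by-meal factorial. The diet-intake text lists its terms in the same style. In that case the overall difference can be estimated from the planned model, and if a week factor has sum-to-zero coding the meal coefficient is already the 12-week average. This largely stands: the gap is an unnamed contrast, not a model that cannot provide one. What remains is that the coding is unstated. Under reference coding the meal coefficient is the difference at week 0 or at one reference week.

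The interaction may also be a question the investigators want answered, since weekly surveys suit the study of adaptation over time. That stands, and it is a reason to keep the interaction beside the averaged contrast.

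The Tukey sentence might be meant to extend to the survey models, which follow it directly. It more naturally belongs to the diet-intake text that it closes. If it does extend, it does not say whether groups are compared within weeks or averaged over them.

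A reader might go further in three ways that the documents do not support.
- That satiety and tolerability will be judged on the interaction alone. No text says so; the plan simply names nothing else.
- That superior satiety is a hypothesis of this trial. The statement that "lentil meals are equally pleasing, produce greater satiety, and are well-tolerated" reports what the method showed in another, ongoing study.
- That the GI model is wrong without a meal-by-symptom term. The survey covers "level of bloating, flatulence, cramping, and comfort", and pooling would dilute an effect confined to one of these. If the symptoms move together it would not, so this is partly a preference about the estimand.

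**Conclusion.** The point holds for the satiety and GI severity models. No overall lentil-control contrast is named, and the interaction that is named is not the treatment effect, because no pre-intervention survey is described. With main effects fitted, the contribution of a constant difference to the interaction is exactly zero. That result needs no assumption about sample size, ICC or effect size. It follows that a non-significant interaction is no evidence of equal satiety or tolerability.

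The power figures are illustrative only, since every input to them is assumed, and the calculation with main effects omitted is an alternative reading of the plan, not an additional loss. The reach is limited: satiety and tolerability are outside the three stated objectives, and the triglyceride and inflammation models list meal group directly.

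**What to change.** Write out the fixed effects for both survey models: week, meal and their interaction (plus symptom type for GI severity), with the coding of week stated. For each satiety measure and for GI severity, report the lentil-minus-control difference averaged over weeks 1-12 with its 95% CI. Report the interaction alongside it as the question of change over time. Base any statement about satiety or tolerability on the averaged difference and its interval.

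The Statistical Plan is written in the past tense. If these analyses have already been run, label the averaged contrast as added after the fact. By-symptom GI differences are an optional secondary refinement; if reported, list the symptom levels and adjust for multiplicity.

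The cost is a few sentences in the SAP and a re-run on survey data that the design already collects, or only the extraction of one contrast if the full factorial was fitted. The downside is a few more reported contrasts.

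### As described, the GI symptom model gives one arm difference shared by all symptoms; add symptom-specific contrasts, and name the average meal difference for satiety

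*Combined protocol and SAP*

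**What the plan says.** Under Dietary intervention, the protocol describes two short online surveys that "will be delivered once a week during the 12-week intervention". The 4 pm survey covers hunger, fullness, satiety and satisfaction. The 8 pm survey covers "gastrointestinal comfort (level of bloating, flatulence, cramping, and comfort) throughout the day". No survey before the intervention is described, and the scoring of the items, including the direction of the comfort item, is not given.

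The Statistical Plan then gives two models:

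- GI symptoms: "GI symptom severity was analyzed through a linear mixed effects model with symptom type and a week and meal interaction as predictors".
- Satiety: "Linear mixed effects models were used to assess the impact of a week and meal interaction on satiety measures".

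For both, "Subject was the random effect for models assessing satiety and GI symptom severity". No symptom-by-meal term is named for the GI model, and no average meal contrast is named for either model. The plan does not say which survey items count as symptom types, or whether week is a factor or a linear trend. The sentence just before the satiety model, at the end of the account of the dietary-intake models, reads in part "Post-hoc multiple pairwise comparisons were performed to detect significant differences by group" and names Tukey's method.

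**The concern.** The survey collects the GI items separately, but the model as described reduces them to one arm difference. If lentil meals raised flatulence and nothing else, the fitted difference would be a fraction of the true one and would be assigned equally to cramping and bloating. A tolerability report from that model could not say which symptom, if any, was responsible.

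For satiety, the only effect named is the week-by-meal interaction. With no pre-intervention survey described, that interaction measures change in the arm difference across the 12 weeks, not the difference itself. Unless the average meal difference is also reported, a reader of a non-significant result cannot tell whether the arms did not differ or whether they differed by a steady amount.

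**Working it through.** The documents give no sample size, standard deviation (SD), scale or effect size for these outcomes, so there is no plan figure to reproduce. The structural results (steps 1 to 3) come from the model form. The power, interval and false-positive figures (step 4 and the simulation in step 3) rest on assumed inputs.

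**1. GI model, one symptom affected.** Inputs from the documents: symptom type as an additive predictor, week and meal interaction, 12 weekly surveys, up to four items. For symptom s, week w and meal m, the mean is: symptom effect(s) + week effect(w) + meal effect(m) + week-by-meal effect(w, m). The arm difference contains no s, so it is the same for every symptom. It can vary by week if week is a factor, or along a straight line if week is linear. With balanced data it equals the mean of the k true symptom differences:

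- k = 4, one symptom affected by d: (d + 0 + 0 + 0)/4 = 0.25d, fitted for all four.
- k = 3, one affected: d/3 = 0.33d, fitted for all three.
- k = 4, all affected by d: 4d/4 = d.

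Noise-free refits with d = 1 returned 0.25, 0.33 and 1.00. With symptom-by-meal added, one affected symptom of four gave 1, 0, 0, 0, and the overall average stayed at 0.25.

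**2. GI model, opposite coding.** If one adverse symptom rises by 1 and comfort, not reverse-coded, falls by 1, the pooled difference is (1 − 1 + 0 + 0)/4 = 0. The refit returned 0 for all four items. With symptom-by-meal added it returned +1 and −1 for the two affected items and 0 for the others.

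**3. Satiety, constant difference c.** The interaction compares the arm difference in one week with that in another: c − c = 0. The meal contrast is c. A noise-free fit with c = 0.5 gave interaction 0 and meal 0.5, with week linear or as a factor. In an illustrative simulation (assumed 30 per arm, between-person SD 1, residual SD 1, 300 runs per setting), the interaction test rejected in 4.7%, 4.7%, 4.0% and 4.3% of runs at c = 0, 0.5, 0.8 and 1.0. The average meal contrast rejected in 5%, 44%, 80% and 96%.

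**4. What symptom-specific contrasts cost and gain.** Assumed: between-person SD 1, subject-by-symptom SD 0.5, residual SD 1, 12 weeks, four symptoms.

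- Variance of a person's pooled mean: 1 + 0.25/4 + 1/48 = 1.083.
- Variance of a person's mean for one symptom: 1 + 0.25 + 1/12 = 1.333.
- At 30 per arm (t = 2.00 on 58 df), 95% half-widths are 2.00 × √(2 × 1.083/30) = 0.54 pooled and 2.00 × √(2 × 1.333/30) = 0.60 per symptom, before multiplicity control.

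Power with d = 0.8 at 20, 30 and 40 per arm:

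| True effect | Test | 20 | 30 | 40 |
|---|---|---|---|---|
| One symptom | Pooled | 9% | 11% | 14% |
| One symptom | That symptom, Holm | 33% | 54% | 71% |
| All four | Pooled | 66% | 83% | 92% |
| All four | At least one symptom, Holm | 55% | 76% | 87% |

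Neither approach is better in both cases.

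The added term also needs the right error. At 30 per arm with subject as the only random effect, the symptom-by-meal mean square has expectation 1 + 12 × 0.5² = 4 with no true effect. The model's pooled residual is about (174 × 4 + 2,618 × 1)/2,792 = 1.19. Here 174 = 58 × 3 is the subject-by-symptom df and 2,792 = 60 × 47 − 28 is the total within-person df. The F ratio is inflated about 3.4-fold, and a nominal 5% test rejects about 50% of the time. At a subject-by-symptom SD of 0.25 the rate is about 20%. Simulation agreed with both, and a test against the subject-by-symptom error stayed at 4% to 6%.

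**The case against.** The strongest reply is that the plan's outcome is overall GI symptom severity, and a pooled contrast is a coherent measure of it. No passage promises a symptom-by-symptom comparison, and when all symptoms move together the pooled test has more power (83% against 76% at 30 per arm in the illustration). This stands. The model is incomplete for a question that the data could answer; it is not wrong for the question it addresses.

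The d/4 figure is also conditional. It needs balanced responses, a common scale and same-direction coding, and the documents confirm none of these.

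On satiety, a reader might infer that the plan can never see a constant arm difference. The documents do not support that. A usual week-by-meal model contains a meal term, and the Tukey sentence directly precedes the satiety sentence and might have been meant to extend to it. If it did extend, it could supply satiety and overall GI contrasts, but still not symptom-specific ones. Nor is a satiety hypothesis stated for this trial: the remark that "lentil meals are equally pleasing, produce greater satiety, and are well-tolerated" reports what the group's other, ongoing study showed. What remains for satiety is that the reported effect should be named.

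**Conclusion.** The GI point holds for the model as described: one arm difference common to all symptoms, and no means of attributing it to any one of them. The dilution is to a quarter (four types) or a third (three types) of an effect confined to one symptom, under the conditions above. Cancellation to zero is possible if comfort is pooled without reverse coding. It would go too far to conclude that the pooled analysis is invalid or that a tolerability problem has been hidden, because the pooled contrast still responds to any net shift in severity.

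The satiety point is mainly a clarification.

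The severity is minor. Satiety and GI symptoms appear in none of the three objectives, and the triglyceride, inflammation and microbiome analyses are not affected. The power, interval and false-positive figures are illustrative and say nothing about this trial's actual precision.

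**What to change.** - State the full formula of each weekly model, including how week enters.
- Keep the pooled GI meal contrast, averaged over symptoms and weeks 1 to 12.
- Add a symptom-by-meal term together with a subject-by-symptom random intercept, and report each symptom's week-averaged meal difference with Holm control across symptoms. Do not add the term with subject as the only random effect.
- State whether comfort is a symptom type and how it is scored. Code all items in the same direction before pooling, or leave comfort out of the pooled score.
- For each satiety item, name the meal difference averaged over weeks 1 to 12 as the reported effect, with meal-by-week secondary.
- The Statistical Plan is written in the past tense, so label the added contrasts post hoc if the survey data have already been analysed.

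No new data are needed. The cost is a change of wording, probably a re-run of the survey models, and somewhat wider symptom-specific intervals (0.60 against 0.54 in the illustration, before multiplicity control). Symptom-specific tests also lose power if all symptoms move together, which is the reason to keep the pooled contrast beside them.
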